1.3. GLOSSARY OF ABBREVIATIONS

AE	adverse event
AESI	adverse event of special interest
BID	twice daily
BLQ	below limit of quantification
CRF/eCRF	case report form/electronic case report form
C-SSRS	Columbia Suicide Severity Rating Scale
CX-8998	investigational product
d	day
ECG	electrocardiogram
EEG	electroencephalogram
EOS	end of study
EOT	end of treatment
ESS	Epworth Sleepiness Scale
FSH	follicle stimulating hormone
GSW	generalized spike and wave
HIV	human immunodeficiency virus
hr	hour
HV	hyperventilation
ITT	intent-to-treat
LLN	lower limit of normal
LLOQ	lower limit of quantification
M01	a primary metabolite of CX-8998
M02	a primary metabolite of CX-8998
M03	a metabolite of CX-8998
M04	a metabolite of CX-8998
MDMA	3,4-Methylenedioxymethamphetamine, ecstasy
MedDRA	Medical Dictionary for Regulatory Activities
mg	milligram
msec	millisecond
n	number of subjects
PK	pharmacokinetic
QTcF	Fridericia corrected QT
SAE	serious adverse event
SERDAS	Seizure-related Disability Assessment Scale
s, SD	standard deviation
t*	critical value from the t distribution
TEAE	treatment emergent adverse events
ULN	upper limit of normal
UM-PDHQ	University of Miami Parkinson's Disease Hallucinations Questionnaire
WHO	World Health Organization

2. OBJECTIVES

2.1. PRIMARY OBJECTIVE

To assess the safety and tolerability of CX-8998 in adolescents and adults with idiopathic generalized epilepsy with absence seizures.

2.2. SECONDARY OBJECTIVES

To evaluate the pharmacokinetics of CX-8998 and its metabolites (including, but not limited to, M01 and M02) in the plasma of subjects with idiopathic generalized epilepsy with absence seizures.

2.3. EXPLORATORY OBJECTIVES

To assess the exposure-response and exposure-safety relationships for plasma CX-8998 and its metabolites (including, but not limited to, M01 and M02); results to be reported separately from the Clinical Study Report.

To evaluate the pharmacodynamic effects of CX-8998 as measured by electroencephalogram (EEG).

3. GENERAL STATISTICAL CONSIDERATIONS

3.1. SAMPLE SIZE AND POWER

Up to 15 eligible subjects will be enrolled in the study and receive CX-8998. The sample size was not based on statistical considerations, but rather chosen to provide preliminary safety and efficacy information on CX-8998 when administered according to this protocol.

3.2. RANDOMIZATION AND MASKING

This is an open-label study.

3.3. HANDLING OF DATA

3.3.1. Strata and Covariates

There are no planned analyses by stratification factors or covariates. Should there be notable differences between the treatment groups for the exploratory efficacy parameters. Analyses may be repeated adjusting for the baseline (i.e., analysis of covariance with effects for treatment and baseline).

3.3.2. Examination of Subject Subsets

Given the relatively small sample size, there are no planned examinations of subsets.

3.3.3. Multiple Testing and Comparisons

No adjustments will be made for multiple testing.

3.3.4. Missing Data and Outliers

Every effort will be made to obtain all data at each scheduled visit from all enrolled subjects. No imputation for missing data will be implemented in this exploratory study.

3.3.5. Imputation of Incomplete Dates

An incomplete date is any date for which either the day, month or year is unknown, but all three fields are not unknown. An incomplete date occurs when the exact date an event occurred or ended cannot be obtained from a subject. For many of the analyses, a complete date is necessary to determine if the event should be included in the analysis (i.e., if the event is treatment-emergent) or to establish the duration of an event. In such cases, incomplete dates may be imputed.

In particular, treatment-emergence for AEs with missing start or stop dates will be defined using the following additional criteria:

- if the start date for a particular event is after the date of first dose, then that event will be considered treatment-emergent;
- if the start date for a particular event is missing and the stop date was after the date of first dose, then that event will be considered treatment-emergent; and
- if both the start and stop dates for a particular event are missing, then that event will be considered treatment-emergent.

‘Concomitant’ for medications or non-drug therapies with missing start or stop dates, will be defined using the following criteria:

- if both the start and stop dates of a particular therapy are missing, then that therapy will be considered concomitant,
- if the start date of a therapy is missing and the stop date of that therapy falls on or after the date of the first dose, then that therapy will be considered concomitant,
- if the start date of a therapy is prior to the date of the first dose and the stop date of that therapy is missing and the therapy was listed as continuing, that therapy will be considered concomitant, and
- if the start date of a therapy is prior to the date of the first dose and the stop date of that therapy is completely missing and the therapy is listed as not continuing, that therapy will be considered not concomitant.

If other missing dates need to be imputed, the project statistician will impute dates in a systematic, but reasonable manner to minimize bias using the following algorithm:

- If the month/year is the same as the Day 1 month/year then the date will be set to the date of Day 1.
- In other cases, missing days will be imputed as the day component of Day 1; missing months/years will be imputed as the month/year of Day 1.

A list of incomplete and imputed dates will be prepared by the project statistician or statistical programmer(s) and will be submitted for review by the clinical project manager and sponsor prior to database lock.

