### Study PN003

Title (population)	A 2-Part, Adaptive Design, Randomized, Double-Blind, Placebo-Controlled Crossover Polysomnogram (PSG) Study to Evaluate the Effects of Single Doses of MK-8998 on Slow Wave Activity and Rapid Eye Movement Sleep in Healthy Middle Aged and Elderly Subjects (28 healthy males, 40-80 years old)
Design	Single oral doses of 4, 8, or 12 mg CX-8998 or placebo prior to bedtime
Summary of findings	
Safety:
 

Single oral doses of 4, 8, or 12 mg CX-8998 were well tolerated

The most common AE's were headaches, vivid dreams, and visual and/or auditory disturbances/hallucinations. The dose of CX-8998 was administered at bedtime for this sleep study. The visual and auditory disturbances/hallucinations were typically described as seeing geometric shapes, colors, lights and/or movement, and hearing tones similar to a telephone or electronic music. These were generally not disturbing to subjects. These events had onset about 30 minutes after dosing or generally near <math>T_{max}</math>, and resolved within minutes or during the night.

PK, PD:

PK data was not yet available for this study

PD, polysomnogram (PSG) study:

- The hypothesis that sleep slow wave activity (SWA) would increase following dosing with CX-8998 was not supported: SWA decreased by 30% after 12 mg of CX-8998; delayed sleep onset and decreased sleep maintenance were also observed after 12 mg single doses of CX-8998
- Results of the PSG study with 4 and 8 mg of CX-8998 are not yet available

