16. A single lead EEG will be bipolarly recorded for 5 days using a wearable EEG patch (Epitel device). The EEG recording will be centrally evaluated by a qualified rater. Subjects will be trained in the use of the device by site personnel and will replace the EEG patch every 7 days. Subjects will receive the device at screening. On Days 8 and 20, the nurse who conducts the home visit will check positioning of the device. The device will be returned on the Day 26 clinic visit. This assessment is based on device availability.
17. The "lifetime" version of the C-SSRS will be used at screening, and the "since last visit" version will be completed at all other visits.
18. The UM-PDHQ is a 20-item clinician-administered questionnaire that quantitatively and qualitatively assesses hallucinations. The UM-PDHQ will be completed for any subject who reports hallucinations.
19. All AEs, irrespective of the relatedness to the study drug, will be captured from the time the ICF is signed through the EOS visit. All AEs should be followed until resolution, for 30 days after onset, for 30 days after the last dose of study drug, until the subject is lost to follow-up, or the subject withdraws consent, whichever occurs first. Serious adverse events (SAEs) will be reported up to 30 days after the last dose of study drug. A follow-up phone call will be made 30 days after the last dose of study drug for evaluation of any SAEs.
20. Concomitant medications and adverse events will be recorded by the visiting nurse on Days 8 and 20.

21. Study drug will be administered in the clinic on the morning of Day 1 and Day 26. Study drug will be administered on an outpatient basis on the evening of Day 1 and Day 26 and on the morning of Day 27.
22. Drug compliance will be assessed by a remote mobile technology monitoring application (AiCure).
23. Evaluation of drug compliance and dosing accuracy will be assessed by the visiting nurse.
24. Subjects will return all remaining study drug (including empty bottles) to the site via a prepaid mailer.

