$$\text{total study drug received (capsules)}/\text{total study drug expected(capsules)} * 100$$

Adverse Event

An adverse event is any unfavorable or unintended sign (including an abnormal laboratory finding), symptom, or disease temporally associated with the use of a medical treatment or procedure that may or may not be considered related to the medical treatment or procedure.

Serious Adverse Event

A serious adverse event (SAE) is any adverse event that results in death, is life-threatening, requires in-patient hospitalization or prolongation of existing hospitalization, results in persistent or significant disability/incapacity, is a congenital anomaly/birth defect observed in any offspring of the subject conceived during treatment with the study drug or is an important medical event.

Treatment-emergent Adverse Event

Treatment-emergent adverse events (TEAEs) are all AEs occurring during the treatment period or a pretreatment event that worsens in intensity during the treatment period.

Laboratory Abnormality

Per protocol, a laboratory abnormality is any clinically significant laboratory abnormality suggesting a disease or organ toxicity and which is of a severity requiring active management (i.e., changes of dose, discontinuation of drug, more frequent follow-up, medical treatment or a diagnostic investigation). Laboratory abnormalities may also be recorded as adverse events. While laboratory values are available in the clinical database, assessment of clinical significance is not captured. As such, for analysis purposes, laboratory abnormalities are considered to be any values that are outside of the reported normal range for a given laboratory test.

Treatment-emergent Laboratory Abnormality

Treatment-emergent laboratory abnormalities are all analysis defined laboratory abnormalities occurring in the treatment period that were not within the normal range at baseline.

Concomitant Medications

Concomitant medications are those medications or non-drug therapies taken on or after the initiation of study drug. This definition includes medications started prior to the initiation of study drug that continue to be used concomitantly with study drug.

Orthostatic Blood Pressure

Orthostatic blood pressure is defined as the difference from recumbent to standing in the systolic and diastolic blood pressure measurements.

Seizure Duration

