5.3.2.3. Adverse Events

Adverse events will be mapped to a Medical Dictionary for Regulatory Activities (MedDRA) preferred term and system organ classification, version 21.0. If a subject experiences multiple events that map to a single preferred term, the greatest severity grade and strongest assessment of relationship to study medication, as determined by the investigator, will be assigned to the preferred term for the appropriate summaries. Adverse events that have a missing severity will be classified as having the greatest severity. Adverse events that have a missing relationship will be classified as having the strongest relationship to study medication.

A summary of TEAEs will be presented to show the number and percentage of subjects with at least one AE, SAE, AESI, related AE, or Grade 3 or higher AE.

The occurrence of TEAEs will be summarized by treatment group using system organ class, preferred term, and severity. Separate summaries of treatment-emergent SAEs, AESI, TEAEs related to study drug, and TEAEs leading to the discontinuation of study treatment, and TEAEs by CX-8998 dose administered will be generated. Adverse events will be assigned to a respective CX-8998 according to the start date of the adverse event.

All TEAEs will be listed for individual subjects. The listing will show both verbatim and preferred terms, along with the system organ class and other data gathered regarding the event. All AEs that have start dates prior to the initiation of study treatment will be excluded from the tables but will be included in the listings.

Determination of treatment emergence will be determined according to the rules outlined in Section 3.3.5.

The following are considered AEs of special interest: increase in seizure frequency, new seizure type, and status epilepticus. Otherwise; seizures are not reported as AEs or SAEs.

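### SAP 5.3.2.3 sends treatment emergence to a missing-date rule that counts only dates after the first-dose date, in conflict with the TEAE definition in SAP 3.3.7

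*SAP*

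**What the plan says.** Four parts of the SAP bear on whether an adverse event (AE) is treatment-emergent.

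- **Definition (3.3.7).** "Treatment-emergent adverse events (TEAEs) are all AEs occurring during the treatment period", or pretreatment events that worsen in that period. The treatment period runs from the first dose through Day 27. Protocol 10.2.1 gives the same definition, with the period ending on Day 26.
- **Missing-date rule (3.3.5).** The lead-in reads: "treatment-emergence for AEs with missing start or stop dates will be defined using the following additional criteria". Bullet 1 is "if the start date for a particular event is after the date of first dose, then that event will be considered treatment-emergent". Bullet 2 applies "if the start date for a particular event is missing and the stop date was after the date of first dose". Bullet 3 counts an event when both dates are missing.
- **Pointer (5.3.2.3).** "Determination of treatment emergence will be determined according to the rules outlined in Section 3.3.5". The sentence does not name 3.3.7 and does not restrict itself to missing dates.
- **Table exclusion (5.3.2.3).** Only AEs that start before study treatment is initiated are kept out of the tables. They remain in the listings.

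The concomitant-medication rule in 3.3.5 treats the parallel case of a missing start differently. It counts the therapy if "the stop date of that therapy falls on or after the date of the first dose".

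**The concern.** Day 1 is by definition the date of first dose, so an event that begins on Day 1 after dosing has a start date equal to that date, not after it. It fails bullet 1, although 3.3.7 makes it a TEAE. A programmer who follows the pointer in 5.3.2.3 literally would leave the flag off, and one who follows 3.3.7 would set it.

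TEAEs are the first-listed endpoint under the primary safety objective, and every TEAE table depends on this flag, including the table by dose administered. Events on the day of first dosing are also among those a safety study most wants to count. In the earlier study PN003 the protocol reports of visual and auditory disturbances: "These events had onset about 30 minutes after dosing". Those were single bedtime doses of 4, 8 or 12 mg in healthy men. They make early onset plausible but say nothing about a rate at the 2 mg starting dose.

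**Working it through.** There is no planned figure to reproduce. The check runs the possible date patterns through the three rules at calendar-date level: the 3.3.5 bullets as written, the 3.3.7 definition (first dose through Day 27), and the 5.3.2.3 exclusion (start before treatment).

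| AE dates | 3.3.5 bullets alone | 3.3.7 definition | 5.3.2.3 exclusion |
|---|---|---|---|
| Start the day before Day 1 | not met | not a TEAE unless it worsens | excluded |
| Start Day 1 after dosing; stop Day 1, Day 2 or missing | **not met** | TEAE | not excluded |
| Partial start in the Day 1 month, if imputed to Day 1 | **not met** | TEAE | not excluded |
| Start Day 2 | met | TEAE | not excluded |
| Start missing, stop Day 1 | **not met** | cannot be decided | cannot be decided |
| Start missing, stop Day 2 | met | cannot be decided | cannot be decided |
| Both missing | met | cannot be decided | cannot be decided |
| Start Day 33 | met | not a TEAE | not excluded |

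**Broad reading (3.3.5 applied alone, as 5.3.2.3 directs).** Every Day 1 post-dose start goes unflagged. SAP 1.2, footnote 21, says "Study drug will be administered in the clinic on the morning of Day 1 and Day 26", with the second Day 1 dose that evening. The 2 mg BID level covers Days 1 and 2, so on this reading 1 of its 2 days, and 2 of its 4 doses, could not yield a TEAE.

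**Narrow reading (3.3.5 only for missing dates, 3.3.7 otherwise).** A Day 1 start with complete dates is a TEAE. Three patterns remain exposed:

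1. Start missing, stop on Day 1. Bullet 2 fails, and 3.3.7 cannot decide without a start date, so the event is left out. An event with less information, both dates missing, is counted.
2. Start on Day 1, stop missing. This lies inside the stated scope of 3.3.5 and meets no bullet. Only 3.3.7 brings it back.
3. Partial start in the month of Day 1. The fallback algorithm in 3.3.5 for other missing dates sets such dates to Day 1. If it is used for AE starts, it produces exactly the date that bullet 1 does not accept.

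**Size per affected subject.** SAP 3.1 allows up to 15 subjects. One subject whose only AE is affected changes the incidence of any TEAE by 1/15 = 0.067, or 6.7 percentage points. With fewer subjects the step is larger; for illustration, 1/10 = 10 points. The number of Day 1 AEs is not given, so the total effect cannot be computed.

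**The case against.** A reader might infer that the SAP requires Day 1 events to be dropped, that such events belong to no category, and that TEAE incidence is therefore biased downward. The documents do not support this.

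The bullets stand in a section on incomplete dates, and their lead-in limits them to AEs with missing start or stop dates and calls them additional. A governing definition exists in 3.3.7, matches the protocol at its starting point, and includes Day 1 after dosing. Each bullet gives a sufficient condition, and none says that other events are not treatment-emergent. The medication list in the same section does contain an explicit negative bullet; the AE list does not. The 5.3.2.3 exclusion removes only events that start before treatment. Incomplete and imputed dates also go to the clinical project manager and sponsor for review before database lock.

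All of this stands, and it means that a downward bias follows only if 3.3.5 is applied alone. It does not remove the problem. The pointer in 5.3.2.3 is unqualified and sits where a programmer will look. The missing-start, Day 1-stop case is left out on either reading. The pre-lock review covers incomplete and imputed dates, so a complete Day 1 date would not come before it.

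**Conclusion.** The SAP is internally inconsistent on Day 1 events and should be corrected. The pointer in 5.3.2.3 and the strict *after* in 3.3.5 conflict with the 3.3.7 definition, with the exclusion sentence in 5.3.2.3, and with the medication rule. Day 1 post-dose events are lost from the TEAE tables only if 3.3.5 is taken as the whole rule. On the narrow reading, one pattern is clearly left out, and the other two depend on 3.3.7 being applied over 3.3.5.

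The total effect is unknown. The figure of 6.7 percentage points or more is a step per affected subject, not an expected bias, and it assumes that the subject has no other TEAE. Because all AEs are listed, the data would be recoverable; the tables would be wrong.

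**What to change.** Three wording changes in the SAP:

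1. In AE bullets 1 and 2 of 3.3.5, replace *after* with *on or after* the date of first dose.
2. In 5.3.2.3, cite the 3.3.7 definition as governing, with 3.3.5 used only for missing or incomplete dates.
3. State that an AE dated Day 1 counts as treatment-emergent unless the record shows that it began before the first dose. This default is needed because AEs are collected from consent onward and protocol 10.2.2.1 specifies an onset date, not a time.

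The cost is a few lines of text and one comparison operator in the AE program. A few pre-dose Day 1 events may be counted as TEAEs. That is the conservative direction, and it fits the SAP's existing practice of counting AEs with both dates missing and assigning missing severity or relationship to the worst category. One consequence should be accepted knowingly: once 3.3.7 governs, a fully dated AE that starts after Day 27 is not a TEAE, whereas bullet 1 alone would have counted it.

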5.3.2.6. Epworth Sleepiness Scale.....	22
5.3.2.7. UM-PDHQ.....	22
5.4. Pharmacokinetic Analyses	23
6. PROTOCOL DEVIATIONS.....	23
7. CHANGES IN THE PLANNED ANALYSES FROM THE PROTOCOL	23
8. REFERENCES.....	24
9. PROGRAMMING CONVENTIONS	25
10. PROPOSED TABLES, LISTINGS, AND FIGURES.....	27

1. **INTRODUCTION**

This document describes the statistical methods and data presentations to be used in the summary and analysis of data from Protocol CX-8998-CLN2-002. Background information is provided for the overall study design and objectives. The reader is referred to the study protocol and electronic case report forms (eCRFs) for details of study conduct and data collection.

1.1. **STUDY OVERVIEW**

CX-8998-CLN2-002 is a Phase 2a, open-label study consisting of a screening period of up to 4 weeks and a 4- dose-titration treatment period to dose of up to 10 mg twice daily (BID) of CX-8998, followed by a 1-week safety follow-up period after the last dose of study medication.

Eligible subjects will receive titrating doses of CX-8998 up to 10 mg BID as follows:

1. Days 1 – 2: 2 mg (1 capsule) BID (4 mg/d);
2. Days 3 – 8: 4 mg (2 capsules) BID (8 mg/d);
3. Days 9 – 14: 6 mg (3 capsules) BID (12 mg/d);
4. Days 15 – 20: 8 mg (4 capsules) BID (16 mg/d);
5. Days 21 – 26: 10 mg (5 capsules) BID (20 mg/d);
6. Day 27: 10 mg (5 capsules) (10 mg/d) (once, morning dose only).

Study drug should be administered with food. Subjects should be instructed to take their daily dose at approximately the same times each day. Consecutive doses should be taken no closer than 10 hours and no later than 14 hours (every 12 hours \pm 2 hours). Subjects will remain under observation for at least four hours post-dosing prior to discharge at Visit 1.

At clinic visits at which PK blood draws are scheduled in the afternoon, subjects will take the morning dose at the appropriate time. Both the time of the morning dose and the time of the PK blood draw will be recorded.

A missed dose (>14 hours since the prior dose) should be skipped and should not be “doubled-up” or “made up”; the next dose should be taken 24 hours from the last administered dose. If the subject experiences emesis following the dose, that dose should not be re-taken; instead the next dose should be taken 24 hours from the last administered dose without emesis. If emesis occurs, the subject should contact the investigator or qualified designee at the study site for guidance on management of the emesis.

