3.3.7. Definitions and Terminology

Age

The age of a subject is defined as the number of whole years between the subject's birth date and the date of informed consent.

Day 1 (Baseline)

Day 1 is the earliest day that study drug is initiated.

Study Day

Study Day is defined relative to Day 1 as follows: Study Day = Date of event – Date of Day 1 +1*(1 if date of event \geq Date of Day 1, 0 otherwise).

Study Visit

Study Visit is the nominal visit as recorded on the eCRF.

Baseline Value

For purposes of analysis, the baseline value is defined as the last non-missing value obtained prior to initiation of study drug.

Change from Baseline

Change from baseline for a given endpoint is defined as the Study Day X value minus the baseline value.

Percent Change from Baseline

Percent change from baseline for a given endpoint is defined as the Study Day X value minus the baseline value, quantity divided by the baseline value, multiplied by 100.

$$\text{Percent Change from Baseline} = (\text{Study Day X} - \text{Baseline})/\text{Baseline} * 100$$

Days on Study

Days on study is defined as the number of days from the date of study drug initiation to the final study visit (includes in home or in clinic assessments).

Completer

A subject is defined as a completer if he/she completes the Day 26 EEG and Day 27 dosing regardless of completing the Day 33 visit.

Treatment Period

The treatment period is the period during which a subject receives study drug (i.e., first dose through Day 27).

Days on Study Drug

Days on study drug is defined as the number of days in the treatment period. The date of the last dose of study drug as recorded on the End of Study Visit form or from the AICure electronic data transfer.

Total Study Drug Expected (capsules)

The total study drug expected is defined as the total number of capsules expected to be taken as recorded from all sources and reported from the AICure system.

Total Study Drug Received (capsules)

The total study drug received is defined as the total number capsules of taken as recorded from all sources and reported from the AICure system.

Total Study Drug Received (mg)

The total study drug received (mg) amount will be multiplied by 2 for subjects receiving CX-8998 to calculate the amount of study drug received in mg (i.e., each capsule is 2 mg).

Treatment Compliance

Treatment compliance will be calculated for each subject as a percentage using the following formula:

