14.3.1.1 Summary of Treatment-Emergent Adverse Events

14.3.1.2 Treatment-Emergent Adverse Events by System Organ Class, Preferred Term, and Greatest Severity

14.3.1.3 Treatment-Emergent Adverse Events Related to Study Drug by System Organ Class and Preferred Term

14.3.1.4 Treatment-Emergent Adverse Events by CX-8998 Dose Administered, System Organ Class, and Preferred Term

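### Used for AE onset, the SAP's partial-date rule puts a day-missing onset at 2 mg BID or after treatment, never on Days 3–27, which distorts the TEAE-by-dose table

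*SAP*

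**What the plan says.** SAP 5.3.2.3 (Adverse Events) ties each event to a dose level through its onset: "Adverse events will be assigned to a respective CX-8998 according to the start date of the adverse event". The word for dose seems to have dropped out of that sentence, but the table list in SAP Section 10 makes the meaning clear: "14.3.1.4 Treatment-Emergent Adverse Events by CX-8998 Dose Administered, System Organ Class, and Preferred Term". This is the only planned AE table by dose.

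SAP 3.3.5 (Imputation of Incomplete Dates) has AE-specific bullets first. They decide whether an event with a missing start or stop date counts as treatment-emergent; they do not give it an onset day. A fallback follows: "If other missing dates need to be imputed, the project statistician will impute dates in a systematic, but reasonable manner to minimize bias". It has two parts. The first is "If the month/year is the same as the Day 1 month/year then the date will be set to the date of Day 1". For all other cases, "missing days will be imputed as the day component of Day 1; missing months/years will be imputed as the month/year of Day 1".

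SAP 1.1 gives the titration: 2 mg BID on Days 1–2, 4 mg on Days 3–8, 6 mg on Days 9–14, 8 mg on Days 15–20, 10 mg on Days 21–26, and one 10 mg dose on the morning of Day 27. SAP 3.3.7 ends the treatment period at Day 27.

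**The concern.** Table 14.3.1.4 needs a start date for every event, and the fallback is the only text in the SAP that can complete a date lacking its day. That rule anchors everything to Day 1. In a trial where dose is a step function of study day, anchoring to Day 1 also anchors to the lowest dose.

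Safety and tolerability is the primary objective, and dose rises in five steps over four weeks. A reader will use this table to see at which step events begin. A rule that moves events systematically to the two-day starting step, or out of the treatment period, would mislead on that question. The SAP states that the fallback is meant to limit bias, so the effect is presumably unintended.

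**Working it through.** **Inputs.** The dose schedule (SAP 1.1), the treatment period and Study Day formula (SAP 3.3.7), and the two fallback rules (SAP 3.3.5). The documents state no figure to reproduce. I take subjects to follow the schedule without dose reduction or early stop.

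**Where the imputed date can fall.** A 27-day course is shorter than the shortest month (28 days), so it touches at most two calendar months.
- Onset in Day 1's month: the date becomes Day 1, which is 2 mg BID.
- Onset in the next month: the date becomes Day 1's day of the month, one month later. Study Day = (length of Day 1's month) + 1, that is 29, 30, 31 or 32. All lie after Day 27.
- If Day 1 falls on the 29th to 31st, the imputed date may not exist (31 June, for example). Setting it to month end or rolling it forward still gives Study Day 29–32.

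Example: Day 1 is 15 May. An onset on 26 May is Study Day 12 (6 mg BID); recorded only as May, it becomes Day 1. An onset on 7 June is Study Day 24 (10 mg BID); recorded only as June, it becomes 15 June, Study Day 32.

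**How often.** Assume Day 1 is uniform over the calendar and true onset is uniform over Days 1–27. An onset on study day *s* falls in the next month with probability (*s* − 1)/30.44, where 30.44 = 365.25/12 is the mean month length.

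| True dose (BID) | Study days | Mean of *s* − 1 | Imputed after treatment | Imputed to 2 mg BID |
|---|---|---|---|---|
| 2 mg | 1–2 | 0.5 | 1.6% | 98.4% |
| 4 mg | 3–8 | 4.5 | 14.8% | 85.2% |
| 6 mg | 9–14 | 10.5 | 34.5% | 65.5% |
| 8 mg | 15–20 | 16.5 | 54.2% | 45.8% |
| 10 mg | 21–27 | 23 | 75.6% | 24.4% |
| All | 1–27 | 13 | 42.7% | 57.3% |

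The bottom row is 13/30.44 = 42.7% and 1 − 0.427 = 57.3%. Enumerating every Day 1 date over the 400-year calendar cycle against all 27 onset days gives the same values, with no imputed date on Days 3–27. The 42.7% includes about 1.8% with a non-existent date.

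Only true 2 mg BID events imputed to Day 1 keep their level: (2/27) × 0.984 = 7.3%. For comparison, 2 mg BID covers 2/27 = 7.4% of treatment days but receives 57% of these events.

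**Sensitivity.** With a 26-day course, as in the current protocol, the mean of *s* − 1 is 12.5, so 12.5/30.44 = 41.1% go after treatment and 58.9% to 2 mg BID. The conclusion does not change.

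**What the SAP leaves open.** It does not say which dose column takes an onset after the last dose. Study Day 29–32 is also treatment-emergent under the 3.3.5 bullet (after first dose) but outside the treatment period that the TEAE definition in 3.3.7 relies on. So it is unclear whether these events enter the table at all.

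**The case against.** The strongest reply is that the SAP never says the fallback is used for dose. SAP 3.3.5 names two purposes for completing a date, inclusion in an analysis and duration, and says only that dates may be imputed. That is fair: the misassignment is the natural reading, not an explicit instruction. But 5.3.2.3 needs a start date and no other rule provides one. If the fallback does not apply, the SAP has no rule for these events, and a sentence is needed either way.

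Second, SAP 3.3.5 sends a list of incomplete and imputed dates to the clinical project manager and sponsor before database lock, and Section 9 keeps partial dates as recorded in the listings. Both make the problem visible, and with up to 15 subjects a reader could check events against the dose change log. Neither gives a better rule for the table.

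Third, few events may be affected. AEs are reviewed on Days 1, 8, 14, 20, 26 and 33 (SAP 1.2), so recall intervals are short, and Protocol 10.2.2.1 defines onset date. This stands as a limit on size.

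Three stronger readings are tempting but unsupported:
- *That no partially dated event can reach 4–10 mg BID.* With the month missing and the day known, the recorded day is kept. If Day 1 is 10 May and onset is the 25th of an unknown month, the result is 25 May, Study Day 16, which is 8 mg BID.
- *That the top dose is made to look safer.* If post-treatment onsets were assigned to the last dose received, completers' Day 29–32 events would enter 10 mg BID. The SAP states no convention, so the direction at 10 mg BID is undetermined.
- *That the safety conclusions as a whole are affected.* The overall, severity, related, serious, discontinuation and special-interest TEAE tables do not use dose at onset.

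**Conclusion.** Wrong as written for this use. On the natural reading of SAP 3.3.5 with 5.3.2.3, an on-treatment AE onset with known month and missing day is placed at 2 mg BID or after the last dose, and never on Days 3–27. That part is calendar arithmetic and needs no distributional assumption.

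Under uniform start dates and onsets, about 57% of such events go to 2 mg BID, 43% go after treatment, and about 7% keep their true level. Table 14.3.1.4 would overstate 2 mg BID and understate 4, 6 and 8 mg BID; the effect at 10 mg BID cannot be determined from the SAP. These percentages apply only to events with a missing onset day. The documents do not give their number; it is probably small, though with up to 15 subjects even a few could alter a dose column.

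**What to change.** Add to SAP 3.3.5 and 5.3.2.3:

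- The Day 1 substitution is not used to assign dose at AE onset.
- For an AE with an incomplete start date, dose at onset is taken from the range of dates compatible with the partial date, the stop date and the dosing record. If the range lies within one dose level, that level is assigned. If it spans more than one, the event is shown in Table 14.3.1.4 in a row labelled 'dose at onset not determinable'.
- If an AE stop date is imputed at all, it must not precede the known start date.

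In the 15 May example, an event recorded as starting in June and stopping on 3 June could only have begun on Study Days 18–20, so it would be assigned to 8 mg BID. The current rule would put it on Study Day 32.

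The cost is a few SAP sentences and one table row, with no change to data collection. The downside is that a few events will appear without a dose level.
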